6 PATIENT SELECTION

6.1 Inclusion Criteria

- Male and Female subjects (Age: 21 years and over) who are medically indicated for UDS testing.

6.2 Exclusion Criteria

- Subjects with significant cognitive deficiency that prevent the subject from giving informed consent
- Subjects suffering from an active bladder infection (not including subjects with asymptomatic bacteriuria)
- Pregnant women
- Subjects with recent (less than 2 weeks) pelvic floor surgery
- Subjects who require the use of a suprapubic catheter

	e·Sense® Clinical Investigation Protocol	CLN-00021-ESNS-PH01-PR-01	Version B
---	---	---------------------------	-----------

6.3 Vulnerable Populations

The targeted subject group is not considered a vulnerable population.

6.4 Recruitment Plans

To satisfy the primary objective, the target enrolment is a minimum of 30 subjects with an attempted UDS study (e·Sense® catheter has made contact with the patient's body). To satisfy the secondary objective, the target enrolment is a minimum 60 subjects with an attempted UDS study (e·Sense® catheter has made contact with the patient's body). In addition, the study sponsor will allow up to 65 subjects (5 additional) during the allowable recruitment and project time given the minimum recruitment goals are met. Please refer to Section 11 for details on sample size determination.

Subjects who are visiting the UDS clinic for their medically indicated UDS test will be approached regarding participation in this study. It is estimated that study-wide recruitment of 60 subjects should take approximately 18 weeks of active recruitment at each site. Recruitment will be monitored by Laborie through scheduled meetings with the site co-ordinator. If the subject signs the informed consent, this will be treated as the point of enrolment.

The minimum number of clinical sites shall be two. The maximum number of sites allowed for this study shall be four. A minimum of 15 subjects per site is required to ensure proper distribution across sites. Once each site has met the minimum recruitment of 15 subjects, the sponsor will be informed. Following this, the site may have the option to continue recruitment until the study-wide maximum is reached, based on the discretion of the sponsor. Additional enrolment following the minimum recruitment goal will be dictated by the final number of sites initiated.

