6.6 Subject Withdrawal

Subjects may withdraw voluntarily from the study at any time, without penalty, or the Investigator may terminate a subject's participation (see Section 5.3). The Investigator will notify the Sponsor when a subject has withdrawn from the study (and if possible, the reason for the withdrawal), and this will be recorded on the subject's CRF. Subjects who withdraw, or those not considered to be part of the primary analysis population, will be allowed to be replaced by another subject should project timelines allow. Subjects will **not** be replaced due to poor results. This also applies in cases in which the subject withdraws his or her consent under data protection law according to Art. 7 GDPR. Please refer to Section 11 Statistical Considerations for further details.

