Power was determined by 10,000 binomial simulations (assuming success rate 100%) for each sample size, and calculation of the proportion of simulations for which the null hypothesis would be rejected based on the lower limit of the 2-sided 90% Clopper-Pearson confidence interval. Analysis of 60 subjects would provide 99% power to rule out a success rate $\leq 95\%$ when the true success rate is assumed to be 100%, based on a 1-sided test with type I error rate of 5%. This study requires a minimum of 60 subjects for adequate power to reject the null hypothesis when the true assumed rate is 100%, however the final sample size will be based on site enrolment capabilities within the project timeline. In addition, the study sponsor will allow up to 65 subjects (5 additional) during the allowable recruitment and project time given the minimum recruitment goals are met. The additional subjects will ensure the desired confidence and reliability levels are met should any data or subjects be excluded from the primary analysis population (See Section 11.5) or if the subject withdraws (See Section 6.6). If the enrolment target is not reached, the exact confidence interval will be calculated for the data available, but no hypothesis test will be conducted.

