11.5 Analysis Population

The primary analysis population to be considered in this study will include enrolled subjects who have been successfully catheterized using the investigational device. Should catheterization fail due to a device deficiency, and/or adverse event, these subjects will still be included in the primary analysis and this information shall be recorded on the subjects' CRF#1 (ESNS-PH01-CRF-01), as well as on the adverse event form (ESNS-PH01-CRF-05), or device deficiency form (ESNS-PH01-CRF-06) as applicable. However, should catheterization fail due to patient factors (i.e. the characteristics of the catheter didn't meet patient anatomical needs, coudé tip required, inappropriate French size), these subjects will be considered as part of the sensitivity analysis population.

All subjects in the primary analysis population will be included in the primary analysis of the hypotheses tests. The sensitivity analysis population will also be analysed as the "intent to treat" population, however results of this population will not dictate success or failure of the study and are meant for comparison purposes only. Data will be analysed as outlined in Section 12.1.

Any subjects who are enrolled but for any reason subsequently withdraw from the study prior to being catheterized with the investigational device, will be excluded from analysis. The justification being they were never touched, and no measurements were made with the investigational device.

	e·Sense® Clinical Investigation Protocol	CLN-00021-ESNS-PH01-PR-01	Version B
---	---	---------------------------	-----------

If any CRFs are found to be incomplete, the study monitor will follow-up as to the reasoning. If for some reason a clinical user is unable to fully complete their questionnaire, the questions they have completed will be included in the analysis. Data will be monitored as the study progresses, refer to Section 6.7 for details pertaining to suspension or premature termination.

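### The secondary target of 60 counts catheter contacts, but the test needs at least 59 analysed subjects, so recruitment can close on target with a test that cannot succeed

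*Combined protocol and SAP*

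**What the plan says.** Several sections bear on how many subjects reach the secondary test.

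- **Target.** Section 6.4: "To satisfy the secondary objective, the target enrolment is a minimum 60 subjects with an attempted UDS study". The same sentence defines an attempt as contact between the catheter and the patient's body. Section 6.4 also says: "If the subject signs the informed consent, this will be treated as the point of enrolment".
- **Analysis population.** Under Section 11.5 the primary analysis population "will include enrolled subjects who have been successfully catheterized using the investigational device". Failures linked to the device or to an adverse event stay in: "Should catheterization fail due to a device deficiency, and/or adverse event, these subjects will still be included in the primary analysis". For failures due to patient factors (anatomy, need for a coudé tip, French size), "these subjects will be considered as part of the sensitivity analysis population", and the results in that population do not decide success. Subjects who "subsequently withdraw from the study prior to being catheterized with the investigational device, will be excluded from analysis". Section 11.5 speaks of hypothesis tests in the plural when it assigns them to the primary analysis population.
- **Power.** Section 11.2.2 gives 99% power for 60 subjects analysed.
- **Buffer and replacement.** Section 11.2.2 permits up to five more subjects, to cover exclusions from the primary analysis population and withdrawals, and says: "The additional subjects will ensure the desired confidence and reliability levels are met". Under Section 6.6, subjects who withdraw or fall outside that population "will be allowed to be replaced by another subject should project timelines allow".
- **Closing and testing.** Section 5.3 leaves the end of recruitment to the sponsor, depending on timelines and on whether the minimum has been recruited. Section 11.2.2 withholds the hypothesis test only if the enrolment target is missed.
- **Timing of analyses.** Section 11.7 counts the first 30 subjects in the primary analysis population. For the secondary analysis it gives only the range 60-65, without a unit.

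**The concern.** A subject in whom catheterization is attempted and fails for patient factors counts toward the 60 in Section 6.4 but not in the test under Section 11.5. The loss is foreseeable: coudé catheters are out of scope (Section 3.1), only 7 Fr catheters are supplied (Section 3.3), and men are eligible (Section 6.1).

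The secondary test has almost no room for such losses. If too few subjects are analysable, a device with no severe complications at all would still miss its pre-specified safety criterion. The rule in Section 11.2.2 that would replace the test by an interval alone would not apply, because the target, as counted, had been reached.

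**Working it through.** **Inputs.** Null rate 95%, with rejection if the one-sided 95% Clopper-Pearson lower limit exceeds 95% (Section 11.2.1). Assumed true rate 100%, one-sided type I error 5%, stated power 99% with 60 analysed (Section 11.2.2). Minimum 60 contacts (Section 6.4), maximum 65 (Sections 2, 6.4 and 11.2.2). The documents state no rate of patient-factor failure.

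**Step 1: the plan's own figure.** With 60 analysed, the null is rejected only if all 60 are free of severe complications. The exact type I error is 0.95^60 = 0.0461. At a true rate of 100%, power is 1^60 = 100%. The stated 99% is close enough, and the difference does not matter here.

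**Step 2: smallest number analysed at which the test can succeed.** With zero events the lower limit is 0.05^(1/n) and the p-value is 0.95^n.

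| Analysed n | Lower limit | p-value | Null rejected |
|---|---|---|---|
| 60 | 0.9513 | 0.0461 | yes |
| 59 | 0.9505 | 0.0485 | yes |
| 58 | 0.9497 | 0.0511 | no |
| 57 | 0.9488 | 0.0537 | no |

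With one event, rejection needs at least 93 analysed; at 65 the lower limit is 0.9291. Within the planned range the test can therefore succeed only with zero events and at least 59 analysed.

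**Step 3: losses that can be absorbed.** Closing at 60 contacts, 60 - 59 = 1 exclusion is tolerable and two are not. Closing at 65 contacts, 65 - 59 = 6 are tolerable and seven are not.

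**Step 4: chance of falling below 59.** Let d be the assumed proportion of contacted subjects lost as patient-factor failures, with losses binomial.

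- At 60 contacts: P(X ≥ 2) = 1 - (1-d)^60 - 60·d·(1-d)^59. For d = 2%: 1 - 0.2976 - 0.3644 = 0.338.
- At 65 contacts: P(X ≥ 7), X binomial(65, d).

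| Assumed d | Closing at 60 contacts | Closing at 65 contacts |
|---|---|---|
| 1% | 12% | <0.1% |
| 2% | 34% | <0.1% |
| 3% | 54% | 0.3% |
| 5% | 81% | 4% |
| 10% | 99% | 48% |

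**The case against.** The plan does foresee exclusions. Section 11.2.2 offers the five extra subjects for this purpose, Section 6.6 permits replacement of subjects outside the primary analysis population, and Section 6.4 has the sponsor monitor recruitment. Used fully, these absorb six exclusions, and at losses of up to 3% they nearly remove the risk. That stands. But both provisions are permissive, and Section 5.3 ties closure to the number recruited and not to the number analysable.

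The population for the secondary test is also not beyond doubt. Section 10.2 refers to primary and secondary analysis populations as described in Section 11.5, but Section 11.5 defines no secondary one. If the secondary test took in every contacted subject, the gap would close. The plural in Section 11.5, and the purpose Section 11.2.2 gives for the buffer, point to the primary analysis population, so this objection calls for a clearer statement and does not dispose of the point.

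The practical loss is limited. The secondary objective (Section 4.2) is to report the rate, and the zero-event lower limit moves only from 95.13% at 60 to 94.97% at 58. The information is nearly the same; the formal conclusion is not.

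A reader might go further in three ways that the documents do not support:

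- **That the 65 is counted at consent, so withdrawals before catheterization use up the buffer.** Consent is the point of enrolment, but in Section 6.4 the five extra subjects follow directly on the 60 attempted studies, and the same unit is the natural reading. Such withdrawals are then outside the count altogether.
- **That every failed catheterization leaves the test.** Failures from device deficiency or adverse event remain in it.
- **That a site may stop at 60.** Sites have a minimum of 15; continuing beyond it, and closing the study, are for the sponsor to decide.

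**Conclusion.** The point holds as a mismatch between the unit of the secondary recruitment target and the unit of the test. Two patient-factor failures among 60 contacts are enough to make success impossible at zero events, with the test still formally due. The chance ranges from 12% at an assumed 1% loss to 99% at 10% if recruitment closes at the minimum, and from under 0.1% to 48% if it runs to 65.

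This rests on three things: the secondary test uses the primary analysis population; the loss rates are assumptions; and the sponsor might close at the minimum, which the plan allows but does not require. The assurance attached to the five extra subjects in Section 11.2.2 is too strong, because their recruitment is optional and not tied to the number analysable. The power calculation itself is sound for 60 analysed. The change should be made, although good use of the sponsor's discretion could avoid the problem without it.

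**What to change.** 1. In Section 11.5, state which population the secondary test uses, and reconcile this with the secondary analysis population mentioned in Section 10.2.
2. In Sections 2, 6.4 and 11.2.2, count the minimum of 60 in subjects of that population, as Section 11.7 does for the first 30, and keep the maximum of 65 in subjects with catheter contact.
3. In Section 6.6, require replacement of subjects outside that population until 60 are analysable or 65 have been contacted.
4. In Section 11.2.2, make the rule for withholding the hypothesis test depend on the number analysed and not on the enrolment target.
5. In Section 11.2.2, say that the extra subjects allow 60 to be analysed with up to five exclusions, in place of the present assurance.

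The cost is a protocol amendment, which goes to the ethics committee and regulatory authorities under Section 15, and up to five more subjects, within the maximum already stated. At high loss rates fewer than 60 may still be analysable when the cap is reached; item 4 then governs what is reported.

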6.5 Informed Consent Process

The ICF used by the Investigator for obtaining the subject's informed consent must be reviewed and approved by the Sponsor, if any changes pertaining to site are changed/modified prior to submission to the appropriate EC for approval/favourable opinion. Once the approval letter is received from EC, the letter must be submitted to the sponsor prior to recruitment of subjects.

The Investigator (according to applicable regulatory requirements), or a person designated by the Investigator and under the Investigator's responsibility, should fully inform the subject of all pertinent aspects of the clinical investigation, including the written information given approval by the Ethics Committee (EC). Any new information in regard to the study or investigational device will be provided to the subject by the site. All documentation given to subjects, including written consent, will be translated into the country's official language for each investigational site. As part of the written Informed Consent Form (ICF), the subject will be informed on the processing of his/her personal data in accordance with Art. 13, 14 GDPR including a relevant declaration of consent to be signed separately.

Prior to a subject's participation in the clinical investigation, the ICF should be signed, full name printed and personally dated by the subject or by the subject's legally acceptable

	e·Sense® Clinical Investigation Protocol	CLN-00021-ESNS-PH01-PR-01	Version B
---	---	---------------------------	-----------

representative, and by the person who conducted the informed consent discussion. A copy of the signed and dated ICF will be provided to the subject.

The study sponsor does not foresee any circumstances where emergency enrolment would occur due to the device indication (it is not used in emergency situations), and the fact that subjects being recruited are attending their UDS appointment as a pre-scheduled visit.

6.6 Subject Withdrawal

Subjects may withdraw voluntarily from the study at any time, without penalty, or the Investigator may terminate a subject's participation (see Section 5.3). The Investigator will notify the Sponsor when a subject has withdrawn from the study (and if possible, the reason for the withdrawal), and this will be recorded on the subject's CRF. Subjects who withdraw, or those not considered to be part of the primary analysis population, will be allowed to be replaced by another subject should project timelines allow. Subjects will **not** be replaced due to poor results. This also applies in cases in which the subject withdraws his or her consent under data protection law according to Art. 7 GDPR. Please refer to Section 11 Statistical Considerations for further details.

7 STUDY PROCEDURE

7.1 Study & Visit Schedule

The study consists of two parts (Clinic Visit & Follow-up). The subject consent and UDS Visit may or may not be condensed to one visit. Refer to Table 3 for details.

Table 3. Visit Schedule.

Evaluation	Clinic Visit	
	UDS Visit	Post-Test
Informed Consent	X	
Inclusion Criteria	X	
Exclusion Criteria	X	
Relevant Medical History	X	
UDS Study	X	
Record any Adverse Events	X	
Complete CRFs 1, 2, 4, 5 for each subject and CRF 3 at the end of each clinic day. Complete CRF 6 (Device Deficiency Form) where applicable.	X	
Complete CRF 7, three to five days post-test.		X

	e·Sense® Clinical Investigation Protocol	CLN-00021-ESNS-PH01-PR-01	Version B
---	---	---------------------------	-----------

7.2 Clinic Visit

- Determine if the subject is eligible for the study.
- Conduct informed consent discussion with the subject and complete signature section.
- Conduct urine sediment or dipstick test.
- Collect relevant medical history and record on the subject's CRF (ESNS-PH01-CRF-02*).
- Collect and record other subject details as required on ESNS-PH01-CRF-01* (weight, height, age, sex, subject condition (neurogenic or non-neurogenic), subject symptoms (storage or voiding), etc.).
- Study personnel will explain what will happen during the UDS test to the subject or subjects' representative.
- Study personnel will prepare UDS equipment, study materials, other sterile disposables and supplies as required for the UDS study and record catheter LOT number information on ESNS-PH01-CRF-01*.
- Follow the investigational device instructions for use to zero, place the catheters and record all necessary pre-test data on ESNS-PH01-CRF-01* (ie. insertion depth in cm, any problems during insertion).
- Record pre-test Pves and Pabd resting pressures in each position: sitting, supine and standing on ESNS-PH01-CRF-01, where patient is able.
- Conduct UDS study including quality checks according to ICS Good Urodynamic Practice⁹ recommendations, ensuring good pressure transmission and catheter positioning wherever possible. A minimum of three quality checks (e.g. beginning, middle and end) must be performed during the study.
 - NOTE: As per ICS Good Urodynamic Practice, cough method is considered the gold standard as the primary quality check method⁹. However, in light of the COVID-19 pandemic valsalva manoeuvre or gentle external pressure on the abdomen can be also considered an acceptable quality check method¹⁷. The cough method still should be prioritized as the accepted gold standard, however should a situation arise where asking the patient to cough may not be appropriate (e.g. high-risk area, hospital policy) then valsalva or external pressure quality check methods can be performed.
- At the conclusion of the UDS test, study personnel will ask subjects to answer questions on urodynamic discomfort/pain experience and record all data on ESNS-PH01-CRF-04*.
- If the subject experiences any adverse events during their UDS test, the details are to be recorded on ESNS-PH01-CRF-05*.
- Review urodynamic tracings post-test, and record the observed Pves and Pabd resting pressures every 100 mL of filling or where pressures are first stable (+/- 50mL) on ESNS-PH01-CRF-01*. Add event markers at each point resting measurements are recorded and complete all other ESNS-PH01-CRF-01 sections*.
- Investigator to complete Investigator Assessment and signature page on ESNS-PH01-CRF-01*.

	e·Sense® Clinical Investigation Protocol	CLN-00021-ESNS-PH01-PR-01	Version B
---	---	---------------------------	-----------

- After completing a day of Urodynamic procedures using the investigational device, the user will fill out the clinical user questionnaire and record all necessary data on ESNS-PH01-CRF-03*.

7.3 Telephone Follow-Up

- Three to five days post-test, site personnel will contact subjects by telephone to check whether any adverse events were experienced post-test. Call details to be documented on ESNS-PH01-CFR-07* and any adverse event information recorded on ESNS-PH01-CFR-05*.

Note: If an adverse event occurs during the study, any follow-up medical intervention prescribed is at the discretion of the Investigator. This information should also be recorded on the subject's CRF (ESNS-PH01-CRF-01*) and adverse event form (ESNS-PH01-CRF-05*).

Note: If a device deficiency occurs during the study, this information shall be recorded on the device deficiency case report form (ESNS-PH01-CRF-06)*.

*All CRF's, with de-identified subject tracings and video images (where applicable) must be sent to the sponsor (Laborie) for data collection/analysis.

7.4 End of Study (EOS)

At the conclusion of their UDS test and clinic visit, the subject is no longer required to undergo any further study-related procedures. Subject follow-up will be performed as described in Section 7.5 below.

Once a site has completed its target recruitment, the sponsor (Laborie) will schedule a time to close-out the site, either in person or by telephone as per the monitoring plan. All study related files will be collected and reviewed for completeness. The EOS is considered the point when all subjects have been followed up and data collection is completed.

7.5 Follow-Up

Study staff will telephone each subject three to five days post-test to inquire about possible adverse events that may have occurred after their UDS test. All follow-up call details will be recorded on the follow-up CRF (ESNS-PH01-CFR-07) and update the subjects' adverse event form (ESNS-PH01-CRF-05), where applicable.

The focus of the follow-up call is to gather information about study-related adverse events, which are adverse events that are possibly, probably or definitely related to the study procedure.

For subjects who did not experience any adverse events or were not experiencing symptoms at the time of their follow-up call, their direct involvement in the study ends at the time of the telephone follow-up call. All subjects who did experience adverse events will be followed until resolution, and this information shall be recorded on the subject's CRF (ESNS-PH01-CRF-01) and adverse event form (ESNS-PH01-CRF-05).

	e·Sense® Clinical Investigation Protocol	CLN-00021-ESNS-PH01-PR-01	Version B
---	---	---------------------------	-----------

In the case of persistent adverse events, regular follow-up will be performed by study staff until resolution, at which point the subject's direct involvement in the study will end. Any follow-up medical intervention prescribed and frequency of future follow-ups to treat an adverse event, will be at the discretion of the Investigator.

Since subjects who experience adverse events are being followed until resolution, the length of time a subject is participating in the study can vary. A subjects participation will end if they report no adverse events at the three to five day follow-up call, or when the reported adverse event has resolved.

Follow-up on any treatment decisions made by the Investigator are not the focus of the present study and will not be followed up. Only adverse events related to the urodynamics procedure or use of the investigational device are the focus of the present study.

